## 2.6 Other general principles

### 2.6.1 Handling of Dropouts or Missing data

All data collected up to the point where the patient drops out will be used for analyses. Missing data will not be imputed.

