### **1.3.1 Definition of Analysis Populations**

*Full analysis set (FAS):* all patients who have at least 1 exacerbation event requiring medical intervention in the 12-month pre-treatment historical control period and who received at least one Volara® treatment.

*Per protocol set (PPS):* all patients in the FAS who do not have any protocol deviations that could impact the primary endpoint.

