#### Deviations that could be considered for exclusion in a PPS analysis

- Treatment errors
- Use of prohibited medication known to influence the primary endpoint
- Key exclusion criteria such as:

- Diagnosis with rapidly progressing NMD such as certain types of Motor Neuron Disease (MND)
- Requirement for continuous mechanical ventilation
- Anticipated requirement for respiratory related hospitalization within the next six months
- History of pneumothorax within past 6 months
- History of hemoptysis requiring embolization within past 12 months
- Home use of OLE therapy within the past 12 months
- Inability or unwillingness to perform OLE therapy or study procedures as required

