### 2.1.2 Study Periods

The study periods include the 12-month pre-treatment historical control period, 6-month pre-treatment historical control period, and the active treatment period.

The active treatment period begins once a subject has started therapy with The Volara® System.

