### 2.1.4 Completion and Discontinuation

A patient is considered to have completed the study when he/she ceases active participation in the study because the patient has, or is presumed to have, completed all study procedures according with the protocol (with or without protocol deviations). Any other cases are classified as discontinuation.

Reasons for completion/discontinuation will be reported on the Completion/Discontinuation electronic case report form (eCRF), including:

- Protocol Violation
- Withdraw Consent
- Lost to Follow-Up
- Adverse Device Effect
- Other

Regardless of the reason, all data available for the patient up to the time of completion/discontinuation should be recorded on the appropriate eCRF.

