## 2.4 Endpoint Analyses

### 2.4.1 Primary Endpoint

The primary endpoint analysis will be carried out on the FAS with a supportive analysis performed on the PPS.

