#### 2.4.1.1 Derivation of Primary Endpoint

Exacerbations of pulmonary disease are defined as changes in respiratory status requiring intervention. Documentation of pneumonia or respiratory infection, change in chest x-ray, changes in requirement for respiratory support necessitating any of the interventions below will be considered an exacerbation of pulmonary disease:

- Hospitalization
- ED Visit
- Unscheduled Antibiotics for Respiratory Infection
- Unscheduled outpatient visit

Pulmonary exacerbation events that occurred during the 12-month pre-treatment period and the active treatment period will be recorded in the data. Pulmonary exacerbation events that occurred prior to the Volara® start date occurred in the pre-treatment period. Pulmonary exacerbation events that occurred on or after the Volara® start date occurred in the active treatment period. The paired difference in pulmonary exacerbation events for each subject will be calculated as follows:

$$\begin{aligned} & \text{Number of pulmonary exacerbations in active treatment period} \\ & - \text{Number of pulmonary exacerbations in 6 months prior to treatment start} \end{aligned}$$

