#### 2.4.1.2 Analysis of Primary Endpoint

The primary endpoint of the study, frequency of exacerbations of pulmonary disease requiring medical intervention, will be analyzed descriptively by study period (active treatment and 6-month pre-treatment) using n, mean, standard deviation, minimum, median, and maximum. The paired difference in the frequency of exacerbations of pulmonary disease requiring medical intervention between study periods (active treatment period - 6-month pre-treatment historical control period) will also be analyzed descriptively with n, mean, standard deviation, minimum, median, maximum and 95% two-sided confidence interval (CIs) for the mean paired difference. All pulmonary exacerbation events that occurred in the 12-month pre-treatment period and the active treatment period will be listed.

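### The primary difference sets a count that stops at exit against a full 6-month control count, so early exits shift the estimate and its 95% CI toward OLE

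*SAP*

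**What the plan says.** SAP 2.4.1.1 defines the primary quantity for each subject as the active-period exacerbation count minus the "Number of pulmonary exacerbations in 6 months prior to treatment start". SAP 2.4.1.2 summarises this difference "between study periods (active treatment period - 6-month pre-treatment historical control period") and puts a two-sided 95% confidence interval on its mean, the only interval in the SAP. Both terms are raw counts.

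The control window is always 6 months. For the active window, SAP 2.1.2 says only: "The active treatment period begins once a subject has started therapy with The Volara® System". No end is given.

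The FAS takes patients with at least one event in the 12-month pre-treatment "historical control period and who received at least one Volara® treatment". It sets no minimum follow-up. SAP 2.1.4 asks that "all data available for the patient up to the time of completion/discontinuation should be recorded on the appropriate eCRF", and SAP 2.6.1 adds: "All data collected up to the point where the patient drops out will be used for analyses. Missing data will not be imputed".

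On analysis sets, SAP 2.4.1 states: "The primary endpoint analysis will be carried out on the FAS with a supportive analysis performed on the PPS". The PPS rule in SAP 1.3.1 comes with a list headed "Deviations that could be considered for exclusion in a PPS analysis".

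Protocol 3.5.2 speaks of comparing a rate of exacerbation between periods. The SAP uses a count, and SAP section 3 declares only the removal of the adherence analysis as a change.

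**The concern.** A subject who leaves after two months contributes two months of active events and six months of control events. With no imputation and no scaling, the four lost months count as free of exacerbations. The control term is never shortened, so the error has one direction: it lowers the active count and favours the device, more so as dropout rises.

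Exits need not be random. Protocol 3.2.2 allows a patient who meets an exclusion criterion to be exited, and one criterion is a need for continuous mechanical ventilation. The study exit section of the protocol also lists death and withdrawal of subjects judged unfit or unsafe to continue. Some exits may therefore follow respiratory worsening.

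The study is a descriptive pilot with no formal test (SAP 1.2.2), so the harm is a biased estimate and interval, not an inflated test. It still matters. This is the primary result, Protocol 3.5.2 intends to look for associations attributable to OLE, and Protocol 3.5.1 expects the data to help define effect size for later studies.

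**Working it through.** **Inputs.** About 70 subjects, a convenience sample (SAP 1.2.2), and 6 months of planned active treatment (Protocol Synopsis, Methods). Neither document gives a dropout share, event rate or standard deviation, so there is no planned figure to reproduce and the inputs below are assumed.

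**Closed form, no true effect.** Let λ be events per 6 months, d the share leaving early, and f the mean fraction of the period observed in leavers.

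- Expected control count: λ
- Expected active count: (1−d)λ + dλf = λ[1 − d(1−f)]
- Expected difference: −λ·d·(1−f)

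Apparent reduction, 100·d·(1−f)%:

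| f | d = 10% | d = 20% | d = 30% |
|---|---|---|---|
| 0.75 | 2.5% | 5% | 7.5% |
| 0.50 | 5% | 10% | 15% |
| 0.25 | 7.5% | 15% | 22.5% |

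At d = 20% and f = 0.5, a true rise of 1/(1 − 0.10) = 1.11, or 11%, would look like no change.

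**PPS.** If the PPS removed a share s of leavers, the remaining dropout share would be d(1−s)/(1−ds). At s = 0.5 (assumed) this is 5.3/11.1/17.6% for d = 10/20/30%. With f = 0.5, a bias of 2.6/5.6/8.8% remains.

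**Truncation alone.** Simulation with n = 70, λ = 1, uniform exit times and no selection on prior events: bias −0.05/−0.10/−0.15 events at 10/20/30% dropout, against a CI half-width of about 0.33. The share of null trials with the CI wholly below zero rises from 2.4% to about 5/9/14%. At 20% dropout it is about 6% for λ = 0.5 and 12–13% for λ = 2.

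**With the entry and FAS rules.** Simulation of 4,000 null trials, n = 70, gamma frailty variance 0.5, 3-week run-in, uniform exits, and a source rate of 1.5 per 6 months. After selection the control mean is 1.99 and the active mean 1.77, so regression to the mean gives 1.77 − 1.99 = −0.22 with nobody leaving. Truncation adds to that. The matched difference is the estimator proposed in the fix.

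| Dropout | Raw difference | Truncation part | CI wholly < 0, raw | Matched difference | CI wholly < 0, matched |
|---|---|---|---|---|---|
| 0% | −0.220 | 0 | 17.0% | −0.220 | 17.0% |
| 10% | −0.313 | −0.090 | 28.2% | −0.223 | 16.8% |
| 20% | −0.393 | −0.175 | 41.6% | −0.217 | 16.1% |
| 30% | −0.481 | −0.266 | 56.6% | −0.214 | 15.1% |

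The closed form agrees: 1.77 × 0.5 × (0.1, 0.2, 0.3) = 0.089, 0.177, 0.266. At a source rate of 0.75 the truncation part is −0.05/−0.10/−0.15, and at 3 it is −0.16/−0.33/−0.49.

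**Informative exit.** Source rate 1.5 in both cases.

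- *Leavers with twice the source rate.* Truncation adds −0.16/−0.32/−0.49 at 10/20/30% dropout. The matched difference is −0.219/−0.202/−0.203, against full-follow-up values of −0.214/−0.193/−0.186. An unmatched comparison of pooled events per time gives −0.282/−0.321/−0.371, so scaling must be done within subject.
- *Exit triggered by events* (probability 0.1 or 0.2 per active event; dropout 15.7% or 28.5%). Truncation adds −0.190 or −0.357. The matched difference is off its full-follow-up value by −0.004 or −0.012.

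**The case against.** The strongest reply is that the endpoint comes from charts, not visits. The Protocol Synopsis says records are reviewed for the 6-month active period, and Protocol Table 1 places chart documentation of exacerbations in the 6-month column. Leaving the study need not close a chart, and if review runs to month 6 for everyone the bias is zero. That is a real condition on this finding. But neither document says review continues after exit, and SAP 2.1.4 and 2.6.1 point the other way. Even full review would not recover time lost to death.

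Second, the net direction of all errors is not established. With no end date, a late final contact could lengthen the active count, and patient-reported events asked about at active-period visits could raise it. Both are fair points, but they are separate from truncation, whose own direction is certain. An end date settles the first.

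Third, the general PPS rule in SAP 1.3.1 excludes any deviation that could affect the primary endpoint, and early exit might be read as one. That is uncertain. The illustrative list includes inability or unwillingness to perform therapy or procedures, but not withdrawal of consent or loss to follow-up, and the PPS is only supportive.

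Fourth, the 28–57% shares of CIs below zero include regression to the mean. They should be read against the 17% zero-dropout baseline or replaced by the truncation-only figures.

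Fifth, SAP 2.2 tabulates discontinuations and lists days in study. But those days run from enrollment, so they include the 2–4 week run-in, and they do not enter the estimate.

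**Conclusion.** The concern holds and should be fixed. On the most natural reading of the SAP, early exits bias the primary mean difference and its interval toward OLE by λ·d·(1−f). With f = 0.5 that is 5/10/15% of the active-period rate at 10/20/30% dropout, and 2.5% to 22.5% over the range examined. The direction follows from the SAP's rules. The size rests on assumed dropout, exit timing and event rates. The bias vanishes if nobody leaves early or if records are reviewed to month 6 for every subject. Regression to the mean from the entry rule is a separate problem, which in the simulation is already −0.22 events at zero dropout.

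**What to change.** - **SAP 2.1.2:** define the active period as 6 months (for example 183 days) from Volara start, with observation ending at the earlier of that day and the last date covered by record review. Give the control window the same length, immediately before start. State whether review continues after exit and how deaths are handled.
- **SAP 2.4.1:** for each subject use active count − control count × (days observed / 183). Report the mean of this divided by the mean observed fraction, as a difference per 6 months, with a subject-level robust or bootstrap 95% CI. Show events and days observed by period.
- **Sensitivity:** give the planned raw difference in subjects with a full 6 months, noting that this set is itself selected if exacerbations lead to exit. A conditional Poisson model with log days observed as offset is optional. Under event-triggered exit its ratio drifted against OLE (0.887 to 0.914, and 0.894 to 0.945).
- **Elsewhere:** report utilization totals per observed time, add days observed from Volara start to the SAP 2.2 listing, and declare the change in SAP section 3.

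**Cost.** SAP wording and one derived variable. If the last date covered by review was not captured, the discontinuation date already used in SAP 2.2 can serve on the natural reading. The estimate equals the planned one for every subject observed for 6 months. The CI is about 2/4/7% wider than with full follow-up at 10/20/30% dropout, and subjects followed longer carry more weight. SAP version 2.0 is dated May 2024 and SAP 2.6.2 describes conduct in the past tense, so this is a late change to an open-label study. Show the planned FAS figure alongside.

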| Inclusion Criteria | 
Patients who meet all the following inclusion criteria will be included in the study:
 
● Documented diagnosis of neurological disorder or NMD● Age 5-80 years● History of one or more respiratory exacerbations in the past 6 months or two or more respiratory exacerbations in the past 12 months, which required unplanned or unscheduled medical intervention.● Ability to perform OLE therapy as directed● Signed informed consent (and assent if minor subject) |
| Exclusion Criteria: | 
Patients who meet one or more of the following exclusion criteria will not be eligible for the study:
 
● Diagnosis with rapidly progressing NMD such as certain types of Motor Neuron Disease (MND)● Requirement for continuous mechanical ventilation● Anticipated requirement for respiratory related hospitalization within the next six months● History of pneumothorax within past 6 months● History of hemoptysis requiring embolization within past 12 months● Pregnancy● Home use of OLE therapy within the past 12 months● Inability or unwillingness to perform OLE therapy or study procedures as required |

PROTOCOL TITLE

Evaluation of Oscillation and Lung Expansion (OLE) using The Volara® System for treatment of respiratory complications in patients with neuromuscular disease in the home setting

Final Protocol

Protocol Number: CR-RR-2020-005

Date: 11May2022

| | |
|-----------------|---|

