| Methods: | 
After enrollment, baseline data including demographics, pulmonary related medical history including acute respiratory-related hospitalizations, ED visits and unscheduled physician office visits, that occurred during the 12 months prior to OLE therapy initiation, will be documented. Pulmonary function tests (PFTs) will be performed. Quality of Life measures, adherence to therapy and satisfaction with therapy data will be collected.
 
Enrolled patients will be started on OLE therapy with The Volara® System. The device will be used within the approved product labeling. This will be the primary airway clearance devices for these patients during the 6 months of the active-treatment study period. Cough therapy such as mechanical insufflation exsufflation (MIE) therapy will be continued if currently prescribed. Other treatments such as high-frequency chest wall oscillation (HFCWO) or chest physiotherapy (CPT) will not be performed during the active treatment period.
 
Following enrollment, completion of a baseline visit, and initiation of OLE therapy, subjects will be seen for 3 follow-up visits. Medical records will be reviewed for the 6-month active treatment study period to document the occurrence of acute respiratory events, documentation will include respiratory related interventions including: number of hospitalizations and hospitalization days, time to first hospitalization, number of courses of antibiotics for respiratory complications, number of ICU admissions and ICU days, and number of outpatient visits (unscheduled Physician's office visit, Urgent Care Visits, ED visits). Respiratory support requirements during the active treatment period will also be documented.
 
The following tests/procedures will be performed/assessed during the active treatment period:
 
• Pulmonary function will be assessed to obtain SVC, PCF, SPO2, and MIP.• A quality-of-life measure will be administered• Adherence to the prescribed therapy regimen will be assessed using the internal therapy log in The Volara® System. |
|-----------------|---|

PROTOCOL TITLE

Evaluation of Oscillation and Lung Expansion (OLE) using The Volara® System for treatment of respiratory complications in patients with neuromuscular disease in the home setting

Final Protocol

Protocol Number: CR-RR-2020-005

Date: 11May2022

| | |
|-----------------------------|--|

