| | 
• Airway Clearance Satisfaction surveys will be conducted. Results from the active treatment period will be compared to the baseline period, during which the subject received his/her regular airway clearance regimen.Any device related adverse events which occur after initial therapy with The Volara® System will be recorded.Any equipment related complaints which occur after initial therapy with The Volara® System will be recorded. |
| Subject Withdrawal: | Subjects may withdraw consent to participate in the study at any time. The subject may also be withdrawn from the study according to investigator judgement regarding the continued health or safety of the subject or related to inability or unwillingness to perform study therapy or procedures. Removal of subjects may occur for any of the following reasons: 
• Subject enrolled in violation of inclusion/exclusion criteria• Inability to tolerate OLE therapy• Adverse event or adverse device effect that occurs during therapy• Physician judgement that the patient is not a good candidate for the study• Inability or unwillingness to perform OLE therapy and data collection maneuvers as directed |
| Statistical Methods: | Descriptive summary statistics will be provided for demographics, the primary and secondary endpoints. Continuous data will be summarized with N, mean, median, standard deviation, min, and max. Categorical data will be summarized with the number and percent of patients in each category. Incidence of adverse device effects (ADEs) will be tabulated. |

PROTOCOL TITLE

Evaluation of Oscillation and Lung Expansion (OLE) using The Volara® System for treatment of respiratory complications in patients with neuromuscular disease in the home setting

Final Protocol

Protocol Number: CR-RR-2020-005

Date: 11May2022

| | |
|--|---|
| | Incidence of device-related complaints will be tabulated. |
|--|---|

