3.2.2 Exclusion Criteria

Patients who meet one or more of the following criteria will be excluded (or will be exited) from the study:

- Diagnosis with rapidly progressing NMD such as certain types of Motor Neuron Disease (NMD)
- Requirement for continuous mechanical ventilation
- Anticipated requirement for respiratory related hospitalization within the next six months
- History of pneumothorax within past 6 months
- History of hemoptysis requiring embolization within past 12 months
- Pregnancy

PROTOCOL TITLE**Evaluation of Oscillation and Lung Expansion (OLE) using The Volara® System for treatment of respiratory complications in patients with neuromuscular disease in the home setting****Final Protocol****Protocol Number:** CR-RR-2020-005**Date:** 11May2022

- Home use of OLE therapy within the past 12 months
- Inability or unwillingness to perform OLE therapy or study procedures as required

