3.3.4 Study Exit Documentation

Study exit data is collected to document the reason participation in the study ended. Reasons for exit from the study include:

- **Completion of the study**
- **Subject inability to tolerate therapy**
- **Subject withdrawal**
This may be voluntary withdrawal on the part of the subject or subject caregiver or withdrawal by investigator for subjects deemed unfit for or unsafe to continue the trial
- **Subject death**

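### Early exits shorten only the active side of the primary comparison: the SAP sets no end to the active period and does not adjust the raw count for time observed

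*SAP*

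**What the plan says.** **Exits.** The Synopsis (Subject Withdrawal) allows removal for intolerance of the therapy, on physician judgement, or for "Adverse event or adverse device effect that occurs during therapy". Protocol 3.3.4 (Study Exit Documentation) lists "Subject inability to tolerate therapy", "withdrawal by investigator for subjects deemed unfit for or unsafe to continue the trial" and death among the reasons for leaving. Stopping the device for intolerance can therefore end study participation.

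**Data after an exit.** SAP 2.6.1: "All data collected up to the point where the patient drops out will be used for analyses", with no imputation. SAP 2.1.4 asks for data to be recorded up to completion or discontinuation. Neither section mentions data from after that point.

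**Analysis set.** The FAS (SAP 1.3.1) needs one exacerbation in the prior 12 months and one Volara treatment. There is no minimum follow-up.

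**Endpoint.** SAP 2.1.2 defines when the active period begins. SAP 2.4.1.1 assigns every event from the Volara start date onward to it, and subtracts the number of events in the 6 months before start from the number in the active period. SAP 2.4.1.2 summarises the paired difference with a two-sided 95% confidence interval. No step divides by time observed.

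**Length of the active period.** The protocol does give one. Synopsis, Methods: "Medical records will be reviewed for the 6-month active treatment study period to document the occurrence of acute respiratory events". Sections 3.3.3.5 and 3.3.3.6 also speak of six months, and Table 1 places the active-period record review in the 6-month column. Protocol 3.5.2 describes the comparison as one of rates.

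**The concern.** The control window lies wholly before treatment, so nothing that happens later can shorten it. An exit after the first treatment can shorten only the active window. The endpoint is a difference of raw counts, so lost months on the active side look the same as prevented exacerbations. Exits for intolerance or worsening may also come from subjects with above-average risk, which would enlarge the loss.

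The same structure applies to admissions, hospital and ICU days, outpatient visits and antibiotic days, although the SAP plans no paired difference or interval for these.

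No error rate is at stake, because there is no hypothesis test. What is at stake is an estimate and interval that favour the device for a reason unrelated to it, in a study that Protocol 3.5.1 offers as a source of effect size for later trials.

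**Working it through.** The plan gives no event rate, exit fraction or power figure to reproduce, and 70 is a convenience sample. What follows is illustration.

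**Inputs.** From the documents: n = 70 (planned enrolment, so the FAS may be smaller), a 6-month control, a nominal 6-month active period, and a 95% two-sided interval for the mean paired difference. Assumed: no device effect, λ events per 6 months, and k subjects leaving at month m with the average rate. I use λ from 0.5 to 2. The low end is the sparsest history that Protocol 3.2.1 admits: one event in 12 months, provided it fell in the last six.

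**Relative loss in the active mean** = (k/70) × (6 − m)/6, whatever λ is.

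| Exit month m | k = 2 | k = 4 | k = 7 |
|---|---|---|---|
| 1.5 | 2.1% | 4.3% | 7.5% |
| 3 | 1.4% | 2.9% | 5.0% |
| 4.5 | 0.7% | 1.4% | 2.5% |

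For k = 7 and m = 3: (7/70) × (3/6) = 0.050. If those who leave have twice the average rate, the entries roughly double.

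**Against the precision of the study.** For independent Poisson counts the interval half-width is t(0.975, 69) × √(2λ)/√70, with t = 1.995.

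| λ | Half-width | Shift, k = 7, m = 3 | Shift / half-width |
|---|---|---|---|
| 0.5 | 0.238 | 0.025 | 10.5% |
| 1 | 0.337 | 0.050 | 14.8% |
| 2 | 0.477 | 0.100 | 21.0% |

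At λ = 1 and m = 3, k = 2 and k = 4 give shifts of 0.014 and 0.029 events, or 4% and 8% of the half-width.

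**Exits triggered by events.** Suppose each exacerbation leads to exit with probability p and the triggering event is counted. At λ = 1 the mean active count is (1 − e^(−p))/p, which is 0.990, 0.975 and 0.952 for p = 0.02, 0.05 and 0.10. The losses are 1.0%, 2.5% and 4.8%, with 1.4, 3.4 and 6.7 of 70 subjects leaving. If rates vary between patients (gamma, mean 1, variance 1) the mean is 1/(1 + p), or 0.980, 0.952 and 0.909. The losses are then 2.0%, 4.8% and 9.1%.

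**Simulation** (n = 70, 20,000 runs, no device effect, exit times uniform over 6 months, λ = 1, 1.5 or 2, Poisson or gamma-Poisson counts):

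| Share leaving | Shift in paired difference | Interval wholly below 0 |
|---|---|---|
| 0% | none | 2.4–2.7% |
| 10% | −5% of λ | 4.8–6.2% |
| 20% | −10% of λ | 8.1–12.8% |
| 30% | −15% of λ | 13.8–23.6% |

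**Check of the remedy.** Replacing the active mean by total active events divided by total observed time, scaled to 6 months, brought the mean difference to between −0.010 and +0.005 in every scenario (4,000 runs each), which is simulation noise. In those scenarios exit was unrelated to the event rate. The rate therefore corrects for exposure but not for exits linked to worsening.

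**The case against.** The best defence is that the SAP rests on the protocol, and the protocol fixes the period at six months and plans record review across it. Much of this stands. A reader might infer from the SAP that the active period has no end at all; the protocol does not support that for subjects who complete. A reader might also take it as settled that data stop at exit. SAP 2.1.4 and 2.6.1 make that the likelier reading, but neither forbids using chart data from later months. What remains is that no text says which rule governs a subject who leaves, so two analysts could obtain different primary results.

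Second, the net direction is not certain. The SAP's open-ended assignment rule could also lengthen the window of completers, which counts against the device. As an assumed example, if 63 of 70 are counted 7 days too long, the active mean rises by (63/70) × (7/182) = 3.5%, comparable with the losses above. Early exit taken alone still favours the device, and the lengthening has the same cure.

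Third, exits are already visible: SAP 2.2 lists reasons and days in study, and SAP 2.5.1.2 tabulates adverse events leading to discontinuation. True, but the primary summary is not corrected for them. The per-protocol set does not help either: it is supportive only, and discontinuation is not a listed ground for exclusion.

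Finally, a tempting stronger reading comes from Protocol 3.2.2, where patients meeting a criterion "will be excluded (or will be exited) from the study". One might infer that a subject who develops a pneumothorax or comes to need continuous ventilation during treatment must be removed. The rest of the documents does not support this. The Synopsis says "Patients who meet one or more of the following exclusion criteria will not be eligible for the study" and gives as a removal reason "Subject enrolled in violation of inclusion/exclusion criteria", and the criterion on home use of OLE could not sensibly apply once treatment has begun. The phrase is best read as ineligibility at entry, and the point does not depend on it.

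**Conclusion.** The concern holds as a cheap improvement. Followed as written, on the likelier reading, the SAP sets a shortened raw active count against a full 6-month control for any FAS subject who leaves early. That moves the paired difference and the utilization counts toward the device.

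The size is unknown. With 2 to 7 of 70 leaving at month 3 at the average rate it is 1.4% to 5.0% of the active mean, which is small beside the interval. It becomes material only with more exits, earlier exits, or exits concentrated in high-risk subjects. The documents give none of these quantities, so every figure rests on assumed rates and exit fractions. In a descriptive pilot this does not undermine the whole analysis, and the simulated interval frequencies should not be read as inflation of a formal type I error.

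**What to change.** Change the SAP only:

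1. **2.1.2 and 2.4.1.1.** Define the active period as exactly 6 months from the Volara start date for every FAS subject, so that events after month 6 are not counted.
2. **2.6.1.** Where consent and records allow, count chart-documented events to month 6 for subjects who stop the device or leave early, in line with the record review in the protocol Synopsis. Apply this to the primary and the utilization endpoints.
3. **Table 14.2.1.1.** Report beside it the number of subjects with an incomplete window and the months missing. Add the exacerbation rate per observed time, scaled to 6 months, next to the raw paired difference. Use pooled events over pooled time. Count time from Volara start: the days in study in SAP 2.2 run from enrolment and so include the run-in.

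Protocol 3.2.2 and the lists of exit reasons need no change. Decisions to stop the device stay with the investigator.

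The cost is a few SAP sentences, additions to one table, and some extra chart abstraction, with any consent or IRB/EC agreement that it needs. SAP version 2.0 is dated 28 May 2024, and 2.6.2 describes study conduct in the past tense. If late abstraction is no longer practical, items 1 and 3 can still be done from dates and events that the plan already records.

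The downsides are that some counted events will fall after the device was stopped, and the active result may look less favourable. The rate row corrects for exposure only, so item 2 is the better protection where subjects leave because they are worsening.
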